#### 4.5 Duration of Therapy

Treatment may continue until one of the following occurs:

- Disease progression  
*Note:* For unconfirmed radiographic disease progression, please see Section 6.7
- Inter-current illness that prevents further administration of treatment
- Unacceptable adverse event(s)
- Pregnancy
- Patient decides to withdraw from study treatment, **OR**
- General or specific changes in the patient's condition render the patient unacceptable for further treatment in the judgment of the investigator

Pembrolizumab is an FDA-approved therapy for metastatic melanoma. In addition, the primary endpoint of the study is correlation between baseline AMT PET parameters and antitumor response by RECIST criteria at 12 weeks. Secondary endpoint is correlation of AMT PET parameters with PFS. It is anticipated that a considerable number of patients will have durable responses to therapy. To balance between study endpoints, sufficient follow up time, and resources patients who have had clinical benefit (complete response, partial response, stable disease) and can receive pembrolizumab per standard of care (not as part of protocol treatment).

#### 4.6 End of Treatment

End of treatment visits can occur under the following circumstances:

-Patients permanently stop study treatment for disease progression or investigator/patient preference. Such visits should be performed 30 days ( $\pm 7$  days) after the last dose of pembrolizumab.

-Patients have on ongoing  $\geq$  grade 2 or serious AE (SAE). They should continue to be followed until the event is resolved or deemed irreversible by the investigator.

#### 4.7 Duration of Follow Up

Subjects will be followed for up to 3 years after removal from study treatment or until death, whichever occurs first. Patients removed from study for unacceptable adverse events (AEs) will be followed until resolution or stabilization of the event(s).

The long-term follow-up visit is defined as 90 days ( $\pm 15$  days) after the last dose of treatment (see Section 6.1). All adverse events should be followed until this initial long-term follow-up visit (90 days after last pembrolizumab dose).

Subsequent follow-up visits, defined as every 90 days thereafter ( $\pm 15$  days) for up to 3 years or until death (whichever is first) may be conducted via telephone or

chart review. These visits will be limited to history of any subsequent cancer treatments, an assessment of any SAE's considered to be possibly or probably related to study treatment until resolution, and survival status.

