## 2.4 Secondary Endpoints

- 2.4.1 Assessment of PFS, defined as D1 of treatment until progression or death from any cause in patients with metastatic melanoma treated with pembrolizumab as front-line therapy.
- 2.4.2 Correlate tumor lesions imaged at baseline by C11-AMT PET with whole body CT scan with IV contrast (CTIVC).
- 2.4.3 Correlate tumor lesions imaged at baseline by C11-AMT PET with whole body F-FDG PET at baseline and at 12 weeks (or earlier, if patient progresses).
- 2.4.4 Perform immune score, IHC, and/or immunofluorescence to detect underlying host-immune response, expression of components of the IDO pathway (LAT1, IDO, TPH1), lymphocyte subtypes (CD4, CD8, FoxP3, MDSC), PD-1/PD-L1, and other immune checkpoint pathways (LAG3, GITR, TIM3) in freshly collected and archived tumor specimens from patients who will receive pembrolizumab. Correlate immune score and other IHC with SUVmax of the previously imaged lesion by C11-AMT PET.

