A window of  $\pm 2$  days will apply to all study visits including treatment visits. CBC w/diff, chemistry, and LFTs on day 1, cycle 1 of pembrolizumab will be repeated only if  $>7$  days have elapsed between screening laboratory tests and day 1.

Study-related treatment with pembrolizumab is 12 weeks (or earlier if patient progresses). The end of study treatment visit should occur under the following circumstances: (1) Patients permanently stop pembrolizumab for disease progression or investigator/patient preference. Such visits should be performed 30 days ( $\pm 7$  days) after the last dose of pembrolizumab. (2) Patients who have an ongoing  $\geq$  grade 2 or serious AE (SAE) should be followed until the event is resolved or deemed irreversible by the investigator. (3) Patients who are still experiencing clinical benefit (partial response, complete response, disease stability) after 12 weeks of pembrolizumab treatment will discuss with their clinician to continue pembrolizumab as per standard of care (i.e., off study-related treatment but follow up will continue as specified in Section 6.4), especially if they are tolerating treatment well (i.e., are experiencing no ongoing SAEs), wish to continue receiving pembrolizumab.

The first long-term follow-up visit is defined as 90 days ( $\pm 15$  days) after the last dose of on-study treatment. Serious adverse events (SAEs; or follow-up to any SAEs) that occur within 90 days of the end of pembrolizumab (or prior to start of new anti-cancer therapy, whichever is earlier) or any grade of Events of Clinical Interest (see section 7.3 that occur within 90 days of the end of pembrolizumab or 30 days after the initiation of a new anti-cancer therapy (whichever is earlier) must be recorded. Subsequent follow-up visits, defined as every 3 months (90 days) thereafter ( $\pm 15$  days) for up to 3 years or until death (whichever is first) may be conducted via telephone or

chart review. These follow up visits will be limited to history of any subsequent cancer treatments, an assessment of any SAE's considered to be possibly or probably related to pembrolizumab treatment until resolution, date of disease progression on pembrolizumab, and survival status.

Complete history at baseline, physical exam to include height (baseline only), weight and vital signs (BP, respiratory rate, and temperature).

Hgb, ANC, and platelets

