Serum chemistries and electrolytes to include sodium, potassium, bicarbonate, chloride, LDH, BUN, serum creatinine, glucose, calcium, magnesium, total protein, albumin.

LFTs include total bilirubin, AST and ALT.

Thyroid panel includes TSH, T3 and free T4. This test should be performed at screening, D1 of cycle 3, and at the end of treatment.

A urine or serum pregnancy test ( $\beta$ -hCG) is required for all women of childbearing potential at screening within 14 days of the C11-AMT scan and 72 hours before the first dose of pembrolizumab.

Optimal radiographic tumor imaging for baseline clinical purposes includes whole body CT scan (chest, abdomen, and pelvis; add neck, if clinically necessary) with IV contrast coregistered with whole body F-fluorodeoxyglucose (FDG) PET. Brain MRI (or head CT with IV contrast, if MRI is not applicable) is not required at screening if it has been performed within 8 weeks from C11-AMT imaging and was negative for parenchymal brain metastases or leptomeningeal disease. Tumor imaging requirements at screening may be adjusted to take into account the type of tumor imaging done before study enrollment (i.e. whole-body CT scan –chest, abdomen, and pelvis; add neck, if applicable- with IV contrast alone or whole body FDG PET coregistered with CT scan without IV contrast) in relation with timing of C11-AMT PET imaging or pembrolizumab initiation. See section 4.1 for details. Scans for disease assessment will be done at baseline and week 12 (or earlier if patient progresses). If patients continue to have clinical benefit (complete response, partial response, disease stability) after 12 months from pembrolizumab treatment they can continue to be imaged per standard of care.

CT scan of the chest abdomen and pelvis (add neck, if applicable) will be performed twice at baseline: (A) coregistered with FDG PET; in this case IV contrast will be administered, (B) coregistered with C11-AMT PET; in this case no IV contrast will be administered with CT and radiology report will be issued for clinical assessment of tumor burden.

Limited (i.e. not whole body; at least 1 bed position) scan will be performed as described in sections 4.1.1 and 4.1.2 and before fresh tumor biopsy.

Observer-rated toxicity will be assessed using the NCI-CTCAE v4.03

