#### 6.4 Long-term follow up (90 days after week 12 dose of pembroluzimab)

Clinical evaluation: focused history on symptoms/toxicity.

Toxicity: Per NCI CTCAEv4.03; Serious adverse events (SAEs; or follow-up to any SAEs) that occur within 90 days of the end of pembrolizumab (or prior to start of new anti-cancer therapy, whichever is earlier) or any grade of Events of Clinical Interest (see section 7.3) that occur within 90 days of the end of pembrolizumab or 30 days after the initiation of a new anti-cancer therapy (whichever is earlier) must be recorded.

Survival analysis:

**Note:** Subsequent follow-up visits to occur every 90 days ( $\pm$  15 days) for up to 3 years or until death (whichever is first) may be conducted via telephone or chart review, and will be limited to history, date of progression on or following pembrolizumab therapy, if any subsequent cancer treatments were given, an assessment of any SAE's considered to be possibly or probably related to study treatment until resolution, and survival status.

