## **6.7 Assessment of Efficacy**

Subjects who have completed C11-AMT PET, FDG PET and CT scan of the neck, chest, abdomen, and pelvis and have received at least 2 doses of pembrolizumab will be evaluable for assessment of response and progression. Subjects whose cancer growth is documented by physical examination without imaging confirmation will count as progression. Patients who end study therapy for any reason (e.g., toxicity of treatment, decide to withdraw) will still be followed for PFS and OS.

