## 8.3 Data Analysis Plans

Apart from comparing the means of baseline FDG PET and C11-AMT PET SUVmax in responders and non-responders we will fit logistic a regression model with responder status as outcome and AMT PET SUVmax as a covariate. We will also model time-to-progression as a function of C11-AMT PET using Cox model. These analysis will be repeated with k3 as an outcome.

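### The follow-up lists in 4.7, footnote 4 and 6.4 conflict on whether progression is recorded after study treatment, so capture of PFS depends on which one a site follows

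*Combined protocol and SAP*

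**What the plan says.** **The endpoint.** Section 2.4.1 gives the secondary endpoint as "Assessment of PFS, defined as D1 of treatment until progression or death from any cause". Nothing in it depends on whether the patient is still on pembrolizumab. Section 4.5 names the correlation of AMT PET parameters with PFS as a secondary endpoint, and section 8.3 adds: "We will also model time-to-progression as a function of C11-AMT PET using Cox model".

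**The follow-up that must supply the dates.** Section 4.7 sets its length: "Subjects will be followed for up to 3 years after removal from study treatment or until death, whichever occurs first". After the first visit at 90 days, contacts are every 90 days and may be by telephone or chart review. Their content is stated three times:

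- Section 4.7: "These visits will be limited to history of any subsequent cancer treatments", plus related serious adverse events and survival status. Progression is not listed.
- Footnote 4 of the Time and Events Table: a similar restricted list, plus "date of disease progression on pembrolizumab, and survival status".
- Section 6.4, in its note on subsequent visits: a restricted list that includes "date of progression on or following pembrolizumab therapy".

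Section 6.7 states the intention for patients who end study therapy for any reason: they "will still be followed for PFS and OS". It names no data item and no schedule.

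**Imaging.** On-study treatment lasts 12 weeks. Footnote 11 schedules disease-assessment scans at baseline and week 12, or earlier on progression. It then says that patients with continuing benefit "after 12 months from pembrolizumab treatment they can continue to be imaged per standard of care", whereas section 4.2 and footnote 4 place the handover to standard of care at 12 weeks. Section 8 gives no censoring rule for PFS.

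**The concern.** A PFS endpoint that runs beyond treatment needs a progression date that is collected beyond treatment. Study treatment and scheduled imaging both finish at about week 12, so a later progression enters the database mainly through the 90-day contacts. Two of the three texts that define those contacts leave the date out in whole or in part. Section 9.4 has the study teams enter their own data, so two sites could each follow the protocol in good faith and return different PFS data.

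At stake are the PFS estimate and the Cox model in 8.3. A progression that is not recorded becomes an event at death, if death falls within follow-up, or no event at all. Both push estimated PFS upward. Without a censoring rule, a telephone contact could also be taken as evidence that the patient was free of progression on that day.

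**Working it through.** **1. Plan's own figure.** There is none for PFS: no event count, power or precision is stated. The 80% power in 8.2 concerns the primary SUVmax comparison and has no bearing here.

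**2. The texts side by side.** Take a patient who stops early without progression, does not go on to standard-of-care pembrolizumab, and progresses at month 8.

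| Text | Progression date recorded? |
|---|---|
| 4.7 | No |
| Footnote 4, read literally | No, because the patient was off drug |
| 6.4 | Yes |
| 6.7 | Intended, but no data item named |

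Now take a patient who continues standard-of-care pembrolizumab and progresses on it at month 8. Section 4.7 still does not record the date; footnote 4 and 6.4 both do. A gap confined to patients off the drug therefore comes from footnote 4 only. Under 4.7 the gap applies to everyone after study treatment. Survival status is collected under all three lists.

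**3. How much of PFS lies beyond week 12.** Inputs are the median PFS values in section 1.3.2: 4.1 and 5.5 months (the two pembrolizumab arms of the randomized comparison with ipilimumab) and 13.8 months (first-line). I assume exponential times, with week 12 = 84/30.4375 = 2.76 months.

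S(week 12) = 2^(−2.76/median):

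- 4.1 months: 0.627, or 14.4 of 23
- 5.5 months: 0.706, or 16.2 of 23
- 13.8 months: 0.871, or 20.0 of 23

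These are patients still at risk of a later event. With follow-up to 2.76 + 36 = 38.76 months, the share of PFS events falling after week 12 is [S(2.76) − S(38.76)] / [1 − S(38.76)]. That is 63%, 70% and 85% for the three medians.

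The exponential form is rough. It gives 6-month PFS of 2^(−6/5.5) = 47% against the quoted 47.3%, but 2^(−6/4.1) = 36% against the quoted 46.4%.

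**4. What each text would do to PFS (illustration by simulation).** Assumptions: 27 patients, all followed to 38.76 months; exponential PFS; death only after progression, with median post-progression survival 31.1 − 13.8 = 17.3 months; all deaths recorded and counted as PFS events; 10% to 50% of patients stopping the drug without progression by 12 months. Footnote 4 is read literally and 4.7 is taken to record nothing after week 12 except death.

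| Median PFS | Text followed | PFS events | Apparent median (months) |
|---|---|---|---|
| 13.8 | 6.4 | 23.2 | 13.8 |
| 13.8 | Footnote 4 | 21.9 to 17.8 | 14.7 to 22.3 |
| 13.8 | 4.7 | 14.7 | about 35 |
| 5.5 | 6.4 | 26.8 | 5.5 |
| 5.5 | Footnote 4 | 26.1 to 23.7 | 5.7 to 6.8 |
| 5.5 | 4.7 | 20.5 | 18.9 |

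At median 13.8 months under 4.7, about 3.5 progressions carry their true date, 14.7 − 3.5 = 11.2 are dated at death, and 23.2 − 14.7 = 8.5 never appear. Under footnote 4 about 1 to 5 of 23 never appear. Under 6.4 none is lost by the wording.

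**The case against.** The best defence is that the right text already exists. Section 6.4 collects progression on or after pembrolizumab and 6.7 promises PFS follow-up. Footnote 4 and section 6.3.3 both send patients who continue standard-of-care drug to 6.4. The long-term column of the table carries footnote 4, so progression is not absent from the table altogether. Footnote 4's wording may be only a loose way of saying progression after pembrolizumab was started. PFS is a secondary endpoint in an exploratory single-arm study of 27 patients.

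Much of this stands. A reader might infer that PFS will lose events; the documents do not show that, because the loss occurs only where a site or the eCRF follows 4.7 or a literal footnote 4. The cross-references also mean that the footnote 4 rows above, which ignore them, are nearer a worst case for that text. But the cross-references concern patients who continue the drug. They do not settle the matter for patients who stop without continuing, whom footnote 4's wording leaves out, and they do not amend the restricted list in 4.7.

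Three other readings go too far:

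- That the loss is always selective for patients who stop the drug. Under 4.7 it is general.
- That the C11-AMT association is biased in a known direction. Nothing in the documents links stopping without progression to C11-AMT uptake.
- That 14 to 20 of 23 progressions would be missed. Those counts are patients at risk after week 12. They include some who will not progress within follow-up, some whose first event is death, and some whose progression on standard-of-care drug footnote 4 does record.

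**Conclusion.** The conflict is real and should be fixed. PFS is defined without regard to treatment status, and the texts that govern its collection after study treatment range from no progression date (4.7), through a date while on drug (footnote 4), to a date on or after the drug (6.4, supported by the intent in 6.7).

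The consequence is conditional on the text followed. Where it occurs, PFS events are dropped or dated late and PFS tends to be overestimated. Deaths recorded within follow-up recover part of the count but not the dates. They recover nothing for the Cox model if time-to-progression in 8.3 is meant literally, with death not an event. At the cited medians 63% to 87% of patients are exposed to the problem after week 12, on an exponential assumption that fits the 4.1-month arm poorly. The event counts above are an illustration, not a forecast.

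The week-12 response analysis and its power are untouched, so this ranks as a should-fix rather than a threat to the main result. The 12 months in footnote 11 and the 12-week handover elsewhere also disagree; the documents do not establish which is intended, so this can only be flagged for reconciliation.

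**What to change.** Put one follow-up list in 4.7, footnote 4 and 6.4, consistent with 6.7, and have the eCRF follow it. At each contact record:

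- the date and basis (imaging, clinical examination, other) of first progression, whatever the treatment status;
- the dates and results of standard-of-care scans already in the chart since the last contact;
- the start date of any new anticancer therapy;
- survival status.

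In section 8, state that PFS is censored at the last disease assessment, not the last contact, and say whether the Cox model's time-to-progression is the PFS of 2.4.1. Reconcile footnote 11 with section 4.2 and footnote 4 on when imaging passes to standard of care.

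The cost is wording and a few eCRF fields. The information comes from the contacts already planned every 90 days, and no extra scans are needed. Progression dates not collected during follow-up may be hard to recover later, so the lists are best aligned while follow-up is still running.

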#### **4.8 Removal of Patients from Protocol Therapy**

Patients will be removed from protocol therapy and the PI notified when any of the criteria listed in section 4.5 apply. The reason for discontinuation of protocol therapy will be documented on the eCRF.

In case a patient decides to prematurely discontinue protocol therapy (“refuses treatment”), the patient should be asked if she or he may still be contacted for further scheduled study assessments. The outcome of that discussion should be documented in both the medical records and in the eCRF.

Excessive patient withdrawals from protocol therapy or from the study can render the study un-interpretable; therefore, unnecessary withdrawal of patients should be avoided.

#### **4.9 Study Withdrawal**

If a patient decides to withdraw from the study (and not just from protocol therapy) an effort should be made to complete and report study assessments as thoroughly as possible. At the time of withdrawal, the investigator should attempt to establish as completely as possible the reason for the study withdrawal.

- The patient should be asked if they are willing to allow for the abstraction of relevant information from their medical record in order to meet the long term follow up (e.g., survival) objectives outlined in the protocol.
- A complete final evaluation at the time of the patient's study withdrawal should be obtained with an explanation of why the patient is withdrawing from the study.
- If the patient is noncompliant and does not return for an end of study follow up assessment, this should be documented in the eCRF.
- If the reason for removal of a patient from the study is an adverse event, the principal specific event will be recorded on the eCRF.

Excessive patient withdrawals from protocol therapy or from the study can render the study un-interpretable; therefore, unnecessary withdrawal of patients should be avoided.

## 5.0 DRUG INFORMATION

### 5.1 Pembrolizumab

#### 5.1.1 Description

Investigational Clinical Supplies will be provided by Merck as summarized in the table below.

Product Name & Potency	Dosage Form
100 mg/4 mL (25 mg/mL)	Solution

Pembrolizumab (MK-3475) Solution for Infusion is a sterile, non-pyrogenic aqueous solution supplied in single-use Type I glass vial containing 100 mg/4 mL of pembrolizumab (MK-3475). The product is preservative-free, latex free solution which is essentially free of extraneous particulates.

*See the pharmacy manual, provided as a separate document from the protocol.*

#### 5.1.2 Supplier/How Supplied

Pembrolizumab will be provided at no cost to the study patient by Merck, the manufacturer of the drug, for the 12week duration of the study. Clinical supplies will be affixed with a clinical label in accordance with regulatory requirements.

This trial is open-label; therefore, the subject, the trial site personnel, the Sponsor and/or designee are not blinded to treatment. Drug identity (name, strength) is included in the label text; random code/disclosure envelopes or lists are not provided.

#### 5.1.3 Handling and Dispensing

Clinical supplies must be stored in a secure, limited-access location under the storage conditions specified on the label. *See the pharmacy manual, provided as a separate document from the protocol.*

Receipt and dispensing of trial medication must be recorded by an authorized person at the trial site.

Clinical supplies may not be used for any purpose other than that stated in the protocol.

#### 5.1.4 Storage and Stability

*As per the pharmacy manual, provided as a document separate from the protocol.*

#### 5.1.5 Return and Retention

The investigator is responsible for keeping accurate records of the clinical supplies received from Merck or designee, the amount dispensed to and returned by the subjects and the amount remaining at the conclusion of the trial.

Upon completion or termination of the study, all unused investigational product will be discarded at the site per institutional policy (e.g., UNC IDS drug destruction policy). It is the Investigator's responsibility to arrange for disposal of all empty containers, provided that procedures for proper disposal have been established according to applicable federal, state, local and institutional guidelines and procedures, and provided that appropriate records of disposal are kept.

